8 ETHICAL CONSIDERATIONS

This clinical study is designed to comply with International Council for Harmonisation (ICH) Guidance on General Considerations for Clinical Trials and applicable national and local regulations.

8.1 Institutional Review Board/Independent Ethics Committee

It is the responsibility of the investigator to obtain the approval of the IRB/IEC before the start of the study. The investigator will provide Mallinckrodt ARD, Inc. (Mallinckrodt) with a statement of compliance from the IRB/IEC and/or the United States of America (US) Department of Health and Human Services general assurance number. A copy of the approval letter along with a roster of IRB/IEC members and compliance letter and/or the US Department of Health and Human Services general assurance number will be retained as part of the study records. During the course of the study, the investigator will provide timely and accurate reports to the IRB/IEC on the progress of the study at appropriate intervals (not to exceed 1 year) and at the completion of the study. The investigator will notify the IRB/IEC of serious adverse events (SAE) or other significant safety findings per IRB/IEC guidelines. The study protocol, informed consent form (ICF), advertisements (if any), and amendments (if any) will be approved by the IRB/IEC in conformance with international, national and local regulatory requirements; and the CFR, Title 21, Part 56 (where applicable).

8.2 Ethical Conduct of the Study

The study will be conducted in full compliance with applicable international, national and local regulatory requirements; US FDA regulations including 21 CFR 314.106 and 312.120, (where applicable); and ICH guidelines for GCP and in accordance with the ethical principles that have their origins in the Declaration of Helsinki.

8.3 Subject Information and Consent

The ICF must be approved by the sponsor and the IRB/IEC before any subject provides consent. The investigator will provide Mallinckrodt with a copy of the IRB/IEC-approved ICF and a copy of the IRB/IEC's written approval before the start of the study.

At the Screening Visit, subjects will read the ICF and a Health Insurance Portability and Accountability Act (HIPAA) authorization form (if applicable) after being given an explanation of the study. Before signing the ICF and the HIPAA authorization form (if applicable), subjects will have an opportunity to discuss the contents of these forms with study site personnel.

Subjects must assent understanding of and voluntarily sign these forms in compliance with ICH GCP guidelines and 21 CFR, Parts 50 and 312 (where applicable), before participating in any study-related procedures. Subjects will be made aware that they may withdraw from the study at any time. Subjects unable to give written informed consent must orally assent to the procedures, and written informed consent must be obtained from a legally authorized representative in accordance with national and local laws, as applicable.

The ICF must contain all applicable elements of informed consent and the mandatory statements as defined in by national and local regulations including confidentiality. All versions of each subject's signed ICF must be kept on file by the site for possible inspection by regulatory authorities and/or authorized Mallinckrodt personnel. Signed copies of the ICF and the HIPAA authorization form, if applicable, will be given to the subject.

The subjects will be made aware of their right to see and copy their records related to the study for as long as the investigator has possession of this information. If the subject withdraws consent and/or HIPAA authorization, the investigator can no longer disclose health information, unless it is needed to preserve the scientific integrity of the study.

9 BACKGROUND INFORMATION AND RATIONALE

9.1 Overview

First described by Jean-Martin Charcot, amyotrophic lateral sclerosis (ALS) is a progressive neurodegenerative disorder that affects the upper and lower motor neurons in the central nervous system (Goetz, 2000; Mitchell and Borasio, 2007). As upper motor neurons die, there is a loss of communication from the cerebral cortex with symptoms including spasticity and hyper-reflexia. As lower motor neurons die, there is a loss of communication between the brainstem and spinal cord and the muscles, resulting in weakness, muscle atrophy, and fasciculations (Bedlack et al, 2007; Mitchell and Borasio, 2007; Ravits and La Spada, 2009). Symptom expression is dependent on the site of motor neuron loss, with bulbar involvement manifesting as facial weakness, palatal weakness, weakness and fasciculations of the tongue, as well as pseudobulbar symptoms and dysarthria. Limb involvement can start at any spinal level, with spread of motor neuron death typically to the contralateral limb and then through different spinal cord levels (Mitchell and Borasio, 2007; Ravits and La Spada, 2009).

Amyotrophic lateral sclerosis is a relentlessly progressive disease, with mounting disability related to muscle paralysis and eventual death. Although some patients can survive for many years with ALS, up to 70% to 80% die within 5 years of symptoms onset, most commonly due to respiratory failure (Andersen et al, 2005; Beghi et al, 2006; Miller et al, 2009; Mitchell and Borasio, 2007). The incidence of ALS is about 2 in 100,000, and slightly higher in males than

females (Beghi et al, 2006; Berry and Cudkowicz, 2011; Mitchell and Borasio, 2007; Rothstein, 2009). The onset of symptoms in ALS is typically in 5th or 6th decade of life, and onset before 30 years of age is rare (Beghi et al, 2006; Berry and Cudkowicz, 2011; Rothstein, 2009).

In 5% to 10% of patients there is a positive family history for ALS, with a predominant autosomal dominant pattern of inheritance (Berry and Cudkowicz, 2011; Mitchell and Borasio, 2007; Rothstein, 2009). The first genetic mutation linked to familial ALS (fALS) involved the copper/zinc superoxide dismutase (SOD1) gene on chromosome 21, with mutations involving other genes being identified subsequently (Berry and Cudkowicz, 2011; Mitchell and Borasio, 2007; Rothstein, 2009). However, in up to 95% of cases there is no apparent genetic component, a group referred to sporadic ALS (Berry and Cudkowicz, 2011; Mitchell and Borasio, 2007; Rothstein, 2009). The clinical manifestations of fALS and sporadic ALS are similar (Rothstein, 2009), pointing to a potential common mechanism leading to the neurodegeneration.

Clinically, ALS is diagnosed based on patient history, physical examination, and disease course. Ancillary tests such as electrophysiologic studies and neuroimaging can help eliminate other potential etiologies (Berry and Cudkowicz, 2011; Brooks et al, 2000). The El Escorial diagnostic criteria for ALS were developed in the 1990's, subsequently revised to increase sensitivity, and are consensus diagnostic criteria that are typically used in clinical trials (Berry and Cudkowicz, 2011; Brooks et al, 2000; Mitchell and Borasio, 2007; World Federation of Neurology, 1994). The diagnosis of ALS requires the presence of upper and lower motor neuron degeneration as well as the progressive spread of signs or symptoms within a region or to other regions, and importantly the lack of evidence of another disease process that could explain the symptoms. By definition, sensory symptoms must be absent (Brooks et al, 2000; Mitchell and Borasio, 2007).

Clinical research in ALS was relatively sparse until the 1990's. The increase in clinical trials has been spurred by many factors including insights into the potential pathophysiology, development of preclinical and in vitro models and the approval by FDA of a disease modifying treatment (Aggarwal and Cudkowicz, 2008; Berry and Cudkowicz, 2011; Leigh et al, 2004). The pathophysiology of ALS is complex and not well understood. Current theories include abnormal protein aggregation, abnormal RNA processing, abnormal mitochondrial functioning, glutamate excitotoxicity, apoptosis, oxidative stress, and neuroinflammation with microglial activation and T cell infiltration (Bedlack et al, 2007; Berry and Cudkowicz, 2011; Henkel et al, 2009; Lanka and Cudkowicz, 2008; Leigh et al, 2004; Mitchell and Borasio, 2007; Rothstein, 2009).

The discovery of the SOD1 mutations in fALS led to the development of transgenic rodent models that overexpress a specific SOD1 mutation. Subsequent rodent models involving other genetic mutations have also been developed (Lanka and Cudkowicz, 2008; Rothstein, 2009). In vitro models

have also explored the SOD1 mutations, as well as other potential pathophysiologic pathways (Lanka and Cudkowicz, 2008).

Riluzole, approved by FDA in 1995, was shown to have a modest impact on survival in patients with ALS, delaying time to death on average by 2 to 3 months with no change in functional outcomes (Miller et al, 2012; Mitchell and Borasio, 2007; US Department of Health and Human Services, 1995). Riluzole inhibits presynaptic release of glutamate and modulates sodium, potassium, and calcium channels which target neuronal excitation (Bedlack et al, 2007; Bellingham, 2011; Miller et al, 2012). Edaravone was approved by FDA in May 2017, and prior to that it was approved in Japan as a treatment for ALS (FDA, 2017). Edaravone is a free radical scavenger (Kikuchi et al, 2011), and has been shown in 1 controlled 24-week study to delay functional decline in patients with “early ALS” defined by fairly well preserved respiratory function (forced vital capacity [FVC] \geq 80%) and minimal functional decline (Tanaka et al, 2016).

Although some drug development for ALS has been targeted as symptomatic treatment, such as dextromethorphan/quinidine to treat pseudobulbar affect, the majority has been geared towards disease modification with a goal of slowing disease progression. In the 20 years since riluzole was approved, despite advances in elucidating potential pathophysiologic pathways and development of preclinical and in vitro models, only one drug, edaravone, has been shown to impact function and no other drug has been shown to change survival in ALS (Aggarwal and Cudkowicz, 2008; Berry and Cudkowicz, 2011; Gordon and Meininger, 2011; Tanaka et al, 2016). Over 30 agents that target specific potential pathophysiologic pathways implicated in ALS and that had shown promise in preclinical and in vitro models have failed to demonstrate any disease modification (Aggarwal and Cudkowicz, 2008; Berry and Cudkowicz, 2011; Gordon and Meininger, 2011). The reasons for the lack of progress are multifactorial. The discrepancy between improvement in preclinical models and ability to demonstrate benefit in clinical studies suggest possible mechanistic differences between the mouse model and the human disease expression, perhaps due to the relative rarity of fALS, difficulties transitioning from animal models to human studies, or potentially flawed clinical studies (Aggarwal and Cudkowicz, 2008; Lanka and Cudkowicz, 2008). It is clear, however, that there is significant unmet need given the very modest effects of riluzole and lack of any other available treatment option.

As described in the Package Insert, Acthar® Gel (repository corticotropin injection, hereafter referred to as Acthar) contains a highly purified porcine adrenocorticotrophic hormone (ACTH) analogue (Mallinckrodt, 2015). ACTH is a member of the family of structurally related peptides known as melanocortin peptides. Melanocortin peptides, which in addition to ACTH include α -, β -, and γ -melanocyte stimulating hormones, are derived from the natural protein pro-opiomelanocortin and exert their physiologic effects by binding to cell surface G-protein coupled receptors known as melanocortin receptors (MCR) (Buggy, 1998; Mountjoy et

al, 1992). Five subtypes of MCRs have been identified to date (MC1R-MC5R), each with different tissue distributions, binding affinity characteristics, and physiological roles (Getting, 2006). ACTH binds to all 5 subtypes of MCR (Schioth et al, 1995) and recent experiments demonstrate that Acthar also has agonist activity for all 5 MCRs (Mallinckrodt, Unpublished Data).

There are several potential mechanisms by which Acthar may impact the pathophysiologic processes involved in ALS. The MC1R, MC3R, MC4R, and the MC5R are expressed on tissues relevant to ALS, including the cerebral cortex, spinal cord and muscles (Cooray and Clark, 2011; Starowicz and Przewlocka, 2003). Additionally, ACTH has been shown to have neuroprotective and neuroregenerative activities that may also slow the progression of motor neuron death (Starowicz and Przewlocka, 2003; Strand and Kung, 1980). Anti-inflammatory effects are mediated by several mechanisms: the MC1R affects the Nuclear Factor-kappa B pathway leading to downregulation of pro-inflammatory cytokines and chemokines (Ahmed et al, 2013); activation of MC3R and MC4R attenuate pro-inflammatory cytokines, including nitric oxide synthase and nitric oxide (Caruso et al, 2013); and in the microglia, ACTH inhibits production of pro-inflammatory markers such as tumor necrosis factor-alpha, interleukin-6 and nitrous oxide (Delgado et al, 1998).

A pilot study (QSC01-ALS-01; Questcor Pharmaceuticals, 2015) evaluating 4 doses of Acthar (80 Units [U] 2 times per week [2x/week], 24 U daily [QD], 56 U 2x/week, 16 U QD) was completed. This open label study in 43 subjects with ALS demonstrated that Acthar was generally well tolerated, with treatment-emergent adverse events (TEAE) related to either the disease itself or known adverse effects of Acthar. A post hoc case-match control analysis using the Pooled Resource Open-Access ALS Clinical Trials (PRO-ACT) database was conducted. Cases were matched on variables known to predict disease course in ALS, including the ALS Functional Rating Scale (ALSFRS) baseline total score, time from symptom onset to study enrollment, gender, age at symptom onset, site of symptom onset, body mass index, and serum creatinine at baseline (Chiò et al, 2009; Ikeda et al, 2012; Küffner et al, 2015; Stambler et al, 1998; Tysnes et al, 1994). The ALSFRS differs from the ALS Functional Rating Scale-Revised (ALSFRS-R) in that questions assessing respiration (orthopnea, dyspnea, respiratory insufficiency) are not included (Cedarbaum et al, 1999); in accessing the PRO-ACT database, Mallinckrodt discovered that the majority of subjects in the database had ALSFRS assessments as opposed to ALSFRS-R assessments (Mallinckrodt, 2016a). Given this, ALSFRS scores for subjects in QSC01-ALS-01 were generated by excluding Questions 11 and 12 on the ALSFRS-R. In this post hoc analysis, the pooled Acthar treated subjects showed significant separation from the case matched control group on slope of ALSFRS total score change from baseline, suggesting that Acthar may be influencing disease progression.

A second post hoc analysis was conducted to explore the effect of Acthar on functional disease progression as measured by the ALSFRS/ALSFRS-R in patients with ALS. The DREAM Phil Bowen ALS Prize4Life Challenge was issued to promulgate development of algorithms that could predict disease progression in ALS. The algorithm developers were provided with a small subset of data from the PRO-ACT database that included 3 months of individual patient level clinical trial information that was to be used to predict disease progression over the subsequent 9 months (Küffner et al, 2015). There were 37 algorithm submissions each of which was then evaluated on a separate data set from the PRO-ACT database. The 2 winning algorithms both predicted disease progression better than a baseline model and clinicians using the same data (Küffner et al, 2015). Mallinckrodt contacted the developers of 1 of the prize winning algorithms, in order to apply the algorithm to the ALSFRS data generated in Study QSC01-ALS-01. As previously noted, ALSFRS-R scores were converted to an ALSFRS score. Baseline features used as predictors in the algorithm and available in the dataset for QSC01-ALS-01 were selected, and a slope estimate was generated for each subject at Week 36. A comparison of the actual observed slope vs the predicted slope using the algorithm was conducted. The predicted rate of decline was greater than the observed rate of decline in the ALSFRS, again suggesting a potential effect of Acthar on disease progression (Mallinckrodt, 2016a).

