18.3 Medical and Surgical History

Medical and surgical history will be obtained at the Screening Visit. Medical history will include a review of the following systems: general, dermatological, respiratory, cardiovascular, gastrointestinal, genitourinary, gynecological, endocrine, musculoskeletal, hematological, neuropsychological, immune (allergies), and head, eyes, ears, nose, and throat. Historical and current medical conditions including date of last menstrual period for female subjects will be recorded. Subjects will specifically be asked for history of stroke (ischemic, hemorrhagic, other/unknown), dementia (dementia of the Alzheimer's type or other), Parkinson's disease, and/or brain tumor.

In addition, the date of onset and the site (limb, bulbar, or limb and bulbar) of first symptom of ALS will be collected.

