20 STATISTICAL METHODS AND PLANNED ANALYSIS

20.1 General Considerations

This section provides a general description of the statistical methods to be used in analyzing both safety and efficacy data. The key statistical issues or considerations will be addressed. A more detailed statistical analysis plan will be provided in a separate document that will be finalized prior to interim analysis.

Unless otherwise specified, all statistical tests will be two-sided with a significance level of 0.05. Summary statistics will be provided for all study variables with descriptive statistics (number of observations, mean, standard deviation, median, minimum, and maximum) for numerical (or continuous) variables. Frequency and percentages will be calculated for categorical variables. Data summary and analyses will be performed with SAS 9.2 or higher.

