20.5 Efficacy Analysis

20.5.1 Randomized Treatment Period

Summary statistics (n, mean, SD, median, minimum, and maximum) of the baseline value, the value at each scheduled post baseline evaluation, and the corresponding change from baseline for ALSFRS-R score will be presented by treatment group for all subjects in the mITT population and the Per-Protocol population.

ALSFRS-R change from baseline at postbaseline visits will be computed as:

Change = baseline value - postbaseline value

Baseline is defined as the value observed at randomization (Week 0).

The primary efficacy endpoint, change from baseline in the telephone administered ALSFRS-R total score at Week 36 in the Acthar treated group vs the placebo group, will be compared using a mixed model with repeated measures (MMRM) analysis method. ALSFRS-R total score change from baseline will be used as a dependent variable, and the model will include the fixed effects of treatment, visit (categorical covariate), treatment-by-visit interaction, and baseline ALSFRS-R score as continuous covariates. The null hypothesis is that the least squared mean contrast between Acthar and placebo groups at Week 36 equals zero. Significance tests will be based on least-squares means using a two-sided test at $\alpha = 0.05$ (two-sided 95% confidence intervals). An unstructured covariance matrix will be used to model the within-subject variance-covariance. If the unstructured covariance structure matrix results in a lack of convergence, the following tests will be used in sequence: heterogeneous Toeplitz covariance structure, heterogeneous autoregressive covariance structure, and compound symmetry covariance structure. The Kenward-Roger approximation will be used to estimate the denominator degrees of freedom. Least squares mean for each treatment group,

least squares mean difference, and 95% confidence intervals between the treatment groups and the corresponding p-value will be reported.

All “mean slope decline” type of secondary endpoints will be analyzed using random coefficient model. Change from baseline will be the dependent variable, and treatment time (in month, continuous) and treatment-by-time interaction will be fixed effects and intercept will be random effect. Baseline values will be adjusted. Estimates of slope for each treatment group, estimates of slope difference, 95% confidence interval and the corresponding p-value will be reported.

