20.10 Statistical Power and Sample Size Considerations

The primary efficacy analysis will compare the mean telephone administered ALSFRS-R total score change from baseline at Week 36 in the group treated with Acthar to that in the placebo group using mITT analysis population. With 140 mITT subjects in the group treated with Acthar and 70 mITT subjects in the placebo group (210 subjects total), assuming the expected ALSFRS-R total score change from baseline of 6.3 and 9 in Acthar and placebo groups, respectively, the common SD of the ALSFRS-R total score change from baseline at Week 36 of 5.83 (estimated from PRO-ACT database), and dropout rate of 20% prior to Week 36, the study will have at least 80% power to detect the treatment difference at the 0.05 level of significance. Assuming a few subjects might not qualify for the mITT analysis population after randomization, approximately 213 subjects will be enrolled and randomized into Acthar treated group and placebo group in a 2:1 ratio.

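### The primary MMRM could gain precision cheaply by adjusting for prognostic variables that the protocol itself names and collects; at present it uses only baseline ALSFRS-R

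*Combined protocol and SAP*

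**What the plan says.** Section 9.1 describes a post hoc comparison of the open-label pilot with controls from the PRO-ACT database: "Cases were matched on variables known to predict disease course in ALS". The list opens with the baseline ALSFRS total score and continues with "time from symptom onset to study enrollment, gender, age at symptom onset, site of symptom onset, body mass index, and serum creatinine at baseline".

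Each variable is available in this trial before dosing:

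- **Time from onset, site of onset, age at onset:** Section 18.3 says "the date of onset and the site (limb, bulbar, or limb and bulbar) of first symptom of ALS will be collected", at the Screening Visit. With age, the onset date gives the other two time variables.
- **Gender and age:** demographics at Screening (Section 14.1).
- **Body mass index:** height and weight at Screening (Sections 14.1 and 18.6).
- **Creatinine:** part of the chemistry panel (Section 32.1), drawn at Screening and Baseline.
- **Baseline function:** telephone ALSFRS-R at Baseline (Section 14.2).

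Section 20.5.1 and the Synopsis write out the primary model in full. Its fixed effects are "treatment, visit (categorical covariate), treatment-by-visit interaction, and baseline ALSFRS-R score as continuous covariates". No other baseline covariate appears. Section 15.1.1 stratifies randomisation by riluzole use and by an algorithm's predicted decline, split at 1 point per month; neither stratum is in the model.

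**The concern.** Differences in decline that baseline variables can explain stay in the residual error unless the model contains those variables. The Week 36 confidence interval is then wider than the collected data require. This matters more when the design has little power to spare, and Section 20.10 claims only that "the study will have at least 80% power to detect the treatment difference at the 0.05 level of significance". With about 70 placebo subjects, adjustment also guards against chance imbalance in strong prognostic factors. There is a tension as well: the protocol treats these variables as informative enough to match on, and uses a prediction algorithm to stratify, yet the primary model draws on the baseline score alone.

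**Working it through.** **Inputs (Sections 20.1 and 20.10).**

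- The planned changes are "assuming the expected ALSFRS-R total score change from baseline of 6.3 and 9 in Acthar and placebo groups, respectively", so the difference is 9 − 6.3 = 2.7 points.
- The common SD is 5.83. The plan states no covariate adjustment for it; I treat it as the residual SD of the present model.
- mITT subjects: 140 and 70. With 20% dropout, 140 × 0.8 = 112 and 70 × 0.8 = 56 remain at Week 36.
- For the test level, "all statistical tests will be two-sided with a significance level of 0.05".

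**Step 1: reproduce the plan's figure.** SE = 5.83 × √(1/112 + 1/56) = 5.83 × 0.1637 = 0.954. The noncentrality is 2.7 / 0.954 = 2.83. Power from the noncentral t distribution on 166 degrees of freedom is 80.3% (80.8% by normal approximation). The stated figure reproduces.

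**Step 2: add prognostic covariates.** Let R² be the further share of Week 36 variance that the added covariates explain beyond baseline ALSFRS-R. The residual SD becomes 5.83 × √(1 − R²), and the SE shrinks by the factor √(1 − R²). The R² values are assumptions; the documents give none. The last column is the mITT total for 80% power, from the normal-approximation sample size inflated for 20% dropout.

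| Assumed R² | Residual SD | SE | Fall in SE | Power | mITT N for 80% power |
|---|---|---|---|---|---|
| 0 | 5.83 | 0.954 | – | 80.3% | 207 |
| 5% | 5.68 | 0.930 | 2.5% | 82.3% | 201 |
| 10% | 5.53 | 0.905 | 5.1% | 84.3% | 189 |
| 20% | 5.21 | 0.853 | 10.6% | 88.2% | 165 |

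**Step 3: cost in degrees of freedom.** Recomputing with 160 instead of 166 degrees of freedom changes power by less than 0.1 percentage point in every row.

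**Step 4: does the gain survive in a repeated-measures model with dropout?** A simulation used random slopes, nine post-baseline visits, about 20% monotone dropout, an unstructured covariance and 1,500 runs per setting. Across three dropout patterns, adding the predictor cut the empirical SE by 2.2–2.5%, 2.9–5.5% and 8.4–9.6% at R² of 5%, 10% and 20%. That is close to Step 2, or slightly less.

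**Step 5: missing data.** In the same simulation, with dropout depending on the omitted predictor in the Acthar arm only, the model without it was off by 0.08 to 0.19 points (R² from 5% to 40%). The model with it was off by no more than about 0.03. With the same dependence in both arms, errors were at most 0.07 points with either model, and adding the predictor moved the result by only about 0.02. The assumed effect is 2.7 points.

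**The case against.** **Nothing is invalid.** This stands. The contrast is valid under randomisation without further covariates, and the sample size meets its target without them. Matching in the pilot addressed confounding against external controls, so it creates no obligation to adjust in a randomised trial. A reader might infer that the trial is underpowered or its primary analysis wrong; Step 1 shows otherwise.

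**Prognosis is already handled by stratification.** This stands only in part. Stratifying balances a two-level split of predicted decline, but leaving the stratum out of the model forgoes its precision. If the stratum were modelled, much of the gain would follow. For a normally distributed score, a two-level split keeps about 64% of its R² at 50:50 and 58% at 30:70. Going on to the full score would then add about 1.4 to 1.7 power points at R² of 10%, and 2.9 to 3.3 at 20%.

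**The benefit is assumed.** This stands. Section 9.1 speaks of disease course and gives no strength of prediction for Week 36 change. Entry limits (onset within 2 years, FVC of at least 60%) narrow the spread of some predictors. A reader might try to derive an R² from the algorithm's root mean square error of 0.517 in Section 15.1.1. The text does not support this: no units are given, the figure describes the whole algorithm rather than a gain beyond baseline score, and it concerns ALSFRS while the endpoint is ALSFRS-R.

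**Missing data.** A reader might infer that the omission seriously weakens the missing-at-random assumption. It does not. The MMRM already uses up to eight earlier post-baseline scores (Weeks 4 to 32), which track progression directly. Sections 15.4.1 and 22.1 encourage telephone ALSFRS-R after early termination, and Section 20.11 plans sensitivity analyses. Step 5 finds a bias that adjustment removes only when dropout depends on the predictor differently by arm, and even then it is small.

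**The separate SAP may add covariates.** It may, and some efficacy text is redacted. But the primary model is already written out term by term, so a later addition would change it.

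**Conclusion.** The point holds as an inexpensive improvement. Six of the seven predictors named in Section 9.1 are absent from the primary model although the data will be in hand. On the plan's own figures power is 80.3%. Adjustment would bring it to about 82%, 84% or 88% if the added variables explain a further 5%, 10% or 20% of Week 36 variance. Those shares are assumptions, as is reading 5.83 as the residual SD after baseline ALSFRS-R; at the low end the gain is only two points. The case rests on precision, with some protection against chance imbalance. It does not rest on bias, a sample-size error or the algorithm's reported error.

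**What to change.** In Section 20.5.1 and the Synopsis, add a short prespecified covariate set to the primary MMRM. Use one of two options:

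1. time from symptom onset, site of onset and age at onset; or
2. the continuous predicted decline already generated for stratification.

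Enter each covariate with a visit interaction, because a predictor of decline rate has an effect that grows over time. Use the same set for the change-from-baseline secondary endpoints, and keep the present model as a sensitivity analysis. Settle this before any unblinded look; Section 20.1 already requires the SAP to be final before the interim analysis.

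The cost is wording only, with no new data, visits or subjects. Option 1 adds four covariate columns (site has three categories, so two columns). Over nine post-baseline visits that is 4 × 9 = 36 parameters. Option 2 adds 1 × 9 = 9. The loss of degrees of freedom for the Week 36 contrast is negligible either way. Entering all six omitted variables by visit is more than is needed; if convergence is a worry, option 2 is the lighter choice.
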